4. STUDY DESIGN

4.1. Overall Design

Study 209035 (POLAR) is a Phase IIb, open-label, multicenter rollover study designed to assess the antiviral activity and safety of CAB LA + RPV LA administered every 2 months in approximately 100 adult HIV-1 infected participants from the LATTE study.

Participants who fulfill eligibility requirements will be entered into the study to receive CAB LA + RPV LA Q2M or the oral DTG + RPV regimen for at least 12 months, until commercially available.

Participants currently receiving oral CAB + RPV within LATTE will enter POLAR at Day 1 and choose to either transition to Q2M administration of injectable CAB LA + RPV LA or take oral DTG + RPV daily for 12 months. Eligible participants include those originally randomized to oral CAB + RPV in the Maintenance phase and transitioned to the Extension Phase of LATTE. The first injection visit for POLAR can be performed once the most recent central lab results from LATTE are available and safety parameters have been reviewed, and the LATTE Week 312 visit (close-out visit) has been completed (or Week 324 in the event of unavoidable delays). Participants will continue to receive oral CAB + RPV as scheduled within the LATTE trial until their eligibility for POLAR can be fully evaluated and the participant has chosen the new regimen. If determined to be ineligible for POLAR or participant elects to not participate in the study those participants will be withdrawn from the LATTE study.

Participants in POLAR who successfully complete Week 300 in the LATTE study (without meeting study defined withdrawal criteria) will be given the option to receive either CAB LA + RPV LA (administered Q2M) or oral DTG + RPV daily until study intervention is either locally approved and commercially available within the local sector (including through local public/government health sectors), the participant no longer derives clinical benefit, the participant meets a protocol-defined reason for discontinuation or until development of either CAB LA + RPV LA Q2M is terminated.

Any participant who receives at least one dose of CAB LA and/or RPV LA and discontinues the CAB LA + RPV LA regimen for any reason will enter a 52-week LTFU Phase. Those participants must remain on suppressive HAART for at least 52 weeks after the last dose of CAB LA and/or RPV LA.

[figure not shown]
The primary endpoint for the study is the proportion of participants with HIV-RNA greater than or equal to 50 c/mL at Month 12 as per Food and Drug Administration (FDA) Snapshot algorithm using the Intent-to-Treat Exposed (ITT-E) population.

4.1.1. Evaluable Participants

The target population to be enrolled is HIV-1 infected virologically suppressed (HIV-1 RNA <50 c/mL) participants on stable ART who have completed, at minimum, Week 312 (or Week 324 in the event of unavoidable delays) of the LATTE study. It is anticipated that approximately 100 participants will be enrolled into POLAR (see Section 10.2).

4.1.2. Study Schematic

Figure 1 209035 (POLAR) Study Design Schematic

§ All participants in LATTE administered oral CAB 30 mg + RPV 25 mg

† Access commercially once Q8W is approved

Access longer term via commercial route. Participants will continue to receive DTG + RPV if located in a region where not commercially available.

4.2. Treatment Groups and Duration

4.2.1. Eligibility for the POLAR Study for Participants Entering from the LATTE Study

Informed consent must be obtained prior to any study procedures, including any Day 1 assessment.

All participants with an undetectable HIV-1 RNA (<50 c/mL) at Week 300 in the LATTE study are eligible to enter this study. A single repeat to determine eligibility may be allowed ONLY after consultation with the medical monitor. Participants with HIV-1 RNA ≥ 200 c/mL at Week 300 are not eligible to enter the study and will not be allowed a repeat to determine eligibility. The Day 1 visit of the POLAR study will be performed in parallel with the final closeout visit for the LATTE study, Week 312 or (if contracts have not been finalized and/or institutional review board (IRB) approval has not been obtained by Week 312 in the LATTE study) Week 324.

Result of HIV-1 RNA at Week 300	Action
<50 c/mL	Begin POLAR study at Day 1
≥ 50 c/mL but <200 c/mL	Single repeat allowed only after consultation and approval from medical monitor
Single repeat <50 c/mL	Begin POLAR study at Day 1
Single repeat ≥ 50 c/mL	Cannot begin POLAR and must be withdrawn from the LATTE study; Complete withdrawal visit.
≥ 200 c/mL	Cannot begin POLAR and must be withdrawn from LATTE; Complete withdrawal visit.

Should a participant be allowed a repeat, results of this repeat must be available prior to Day 1 of this study, therefore the time needed for scheduling the Day 1 visit, lab draws and lab analysis should be considered.

In addition to the viral load criteria above, if in the opinion of the Investigator, a participant experiences a significant safety event while taking either CAB or RPV, study eligibility will be determined ONLY in consultation with the medical monitor.

Participants ineligible for this study will be withdrawn from LATTE.

4.2.2. Maintenance Phase (Day 1 up to Commercial Approval)

At the Day 1 visit (the start of the first month of the study), participants will return to the clinic, take the last dose of their oral (CAB 30 mg + RPV 25 mg), and receive the first

CAB LA (600 mg) + RPV LA (900 mg) injections (within 2 hours of the final oral dose of CAB + RPV). The second loading injections will be administered 1 month (Month 2 visit, start of the second month of the study) after initial loading dose (CAB LA 600 mg + RPV LA 900 mg), with subsequent injections (CAB LA 600 mg + RPV LA 900 mg) occurring every 2 months thereafter. The dosing window for the second injection will be -7 days from the projected dosing visit.

After Month 2, a dosing window (± 7 days) for injections is stipulated. Doses outside of the window may be allowed with Medical Monitor approval.

Participants will continue CAB LA + RPV LA until:

- study intervention is locally approved and commercially available,
- the participant no longer derives clinical benefit,
- the participant meets a protocol-defined reason for discontinuation
- the development of either CAB LA or RPV LA is terminated.

Safety and efficacy assessments will be conducted as per the Time and Events schedule (Section 8.1 for more information). Dosing will occur according to the selected regimen.

If the IM dosing regimen (Q2M) is discontinued as a result of an independent data monitoring committee (IDMC) from another study evaluating the same regimen, review any subsequent analysis, or any other programmatic analysis, those participants who have not met any clinical management criteria for discontinuation will be discontinued permanently from the study and will enter into the long-term follow-up (LTFU) Phase of the study.

4.2.2.1. Participants electing to receive oral DTG + RPV once daily

The DTG + RPV oral regimen will be administered in an open-label fashion starting on Day 1 until Month 12. Participants will continue study intervention until:

- study intervention is locally approved and commercially available,
- the participant no longer derives clinical benefit,
- the participant meets a protocol-defined reason for discontinuation

Safety and efficacy assessments will be conducted as per the Time and Events schedule (Section 8.1 for more information). Dosing will occur according to the selected regimen.

4.2.3. LTFU Phase – IM Regimen Only

Any participant who receives at least one dose of CAB LA and/or RPV LA and discontinues the CAB LA + RPV LA regimen for any reason must remain on suppressive HAART for at least 52 weeks after the last dose of CAB LA and/or RPV LA in order to prevent selective pressure on HIV and the potential for selection of resistant mutants.

Investigators must discuss the choice of the follow-up HAART regimen with the Medical Monitor prior to initiating the new regimen with the participant. HAART therapy should be initiated within 8 weeks after the last Q2M injection, however if withdrawn due to virologic failure, HAART should be initiated as soon as virologic

failure is confirmed. Discuss with medical monitor. The LTFU will begin the day of the last CAB LA and/or RPV LA dose and continue for 52 weeks. These participants will not complete a Withdrawal visit, but will instead move directly into the LTFU as per the Time and Events Schedule. In addition, for participants who withdraw during the LTFU, the final visit will be considered the study withdrawal visit.

Participants will be assessed with clinic visits at months 1, 3, 6, 9, and 12 during the LTFU Phase. Female participants of child bearing potential must continue to use adequate contraception methods (see Study Procedures Manual for list of accepted forms of contraception) for the entire year of follow up.

In order to assure that participants have access to HAART during the LTFU, ViiV may supply HAART regionally or reimbursement will be provided as needed during this phase. The LTFU Phase may be shortened or terminated at any time during the study for various reasons, e.g., better understanding of risks of development of resistance as CAB and RPV exposures decline, end of study timings, etc.

This phase is considered study participation and participants will be followed on study during this time. A withdrawal visit is not required for participants who do not complete the LTFU Phase. The participants' last on study visit will be considered as their withdrawal visit.

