- Renal toxicity is met and no compelling alternate cause is identified;
- Corrected QT interval (QTc) >550 msec from three or more tracings separated by at least 5 minutes and considered causally related to IP. *Note: ECGs are not routinely conducted in this study.*
- Grade 4 clinical AE considered causally related to study drug;
- Participant has a Grade 3 or higher rash or Grade 2 rash with evidence of systemic involvement and no compelling alternative cause is identified
- Pregnancy (intrauterine), regardless of termination status of pregnancy.
- Participant withdrew consent

Efficacy data for participants withdrawing from the study will be considered evaluable up to the point at which they are withdrawn using the same criteria for evaluability as for participants who complete the study.

Safety data for all participants who receive any amount of study drug, including participants who withdraw from the study, will be included in evaluations of safety.

If a participant is prematurely or permanently withdrawn from the study, the procedures described in the Time and Events Table for the in-clinic Withdrawal visit are to be performed. An in-clinic Follow-Up visit will be conducted 4 weeks after the last dose of study medication for participants with ongoing AEs, and serious adverse events (SAEs) related & not related to study drug and also any laboratory abnormalities that are considered to be AEs or potentially harmful to the participant, at the last on-study visit.

All data from the Withdrawal visit will be recorded, as they comprise an essential evaluation that should be done prior to discharging any participant from the study.

The following actions must be taken in relation to a participant who fails to attend the clinic for a required study visit:

- a. The site must attempt to contact the participant and re-schedule the missed visit as soon as possible.

- b. The site must counsel the participant on the importance of maintaining the assigned visit schedule and ascertain whether or not the participant wishes to and/or should continue in the study.
- c. In cases where the participant is deemed ‘lost to follow up’, the investigator or designee must make every effort to regain contact with the participant (where possible, 3 telephone calls and if necessary a certified letter to the participant’s last known mailing address or local equivalent methods). These contact attempts should be documented in the participant’s medical record.

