7.1.5.3. Confirmed Virologic Failure

Participants with CVF must be discontinued from study intervention. However, participants who have received at least one dose of CAB LA or RPV LA prior to confirming virologic failure will remain in the study on oral HAART in the LTFU Phase.

A plasma sample from the suspected virologic failure visit as well as Day 1 (if baseline HIV-1 RNA level ≥ 200 c/mL) will be sent for genotypic and phenotypic resistance testing and the result made known to the Investigator when available. A plasma sample from the confirmation visit will be obtained for storage. This sample may be used for possible future analyses, e.g., for genotypic and phenotypic analyses of participants who experience virologic failure.

For all participants who meet CVF, baseline and suspected virologic failure plasma samples with HIV-1 RNA level ≥ 200 c/mL will be analyzed in an attempt to obtain genotype/phenotype data on as many samples as possible. Plasma samples for storage will also be obtained at unscheduled visits including confirmation of CVF. Participants may continue to receive study drug at the discretion of the investigator until results of resistance testing are available at which time the participant must be discontinued from the study. Even if genotype/phenotype data cannot be generated, participant must also be discontinued from the study intervention.

If a participant is prematurely discontinued from the study intervention, the investigator must make every effort to perform the Withdrawal Visit evaluations outlined in the Time and Events. These data will be recorded as they comprise essential evaluations needed to be done before discharging any participant from the study.

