- k. Q2M Injections are 1 x CAB LA 600 mg IM + 1 x RPV LA 900 mg IM. If possible, injections should be spaced approximately 2 cm from one another and from the site of any previous injection and or any injection site reaction. Bring RPV LA to approximately room temperature prior to injecting. Time and location of injection (right or left) as well as needle length used will be collected in the eCRF. **IM dosing is expected to occur during the month in which the participant's projected visit falls (as according to the Day 1 visit). An additional (+ or -) 7 day window from date of projected visit is stipulated for IM dosing. All decisions regarding dose interruption/ resumption must be discussed with the medical monitor in advance.**
- l. Or Long-Term Follow Up
- m. Follow Up Visit - Conduct ~4 weeks after the last dose of IP if not entering Long-Term Follow Up and only if the participant has ongoing AEs or lab abnormalities at the last on-study visit. May be conducted by telephone.

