8.1.3. Time and Events Table for Long Term Follow Up

Procedures for Long-Term Follow Up	Month 1 ^a	Month 3	Month 6	Month 9	Month 12	WD	Notes
HIV Associated Conditions, AE and SAE Assessments, Con Meds	X	X	X	X	X	X	
Every effort should be made to enter participants into the Long-Term Follow Up if they withdraw from or discontinue the study after receiving at least one dose of CAB LA and / or RPV LA.
 
a) The start of the 52-week follow up period begins the day of the last CAB LA and/or RPV LA dose.
 
b) Women of childbearing potential only. S = Serum
 
c) Fast overnight; however, a minimum of a 6 hour fast is acceptable.
 
d) Women of childbearing potential should continue to receive counselling on the need to use adequate contraception for the entirety of the Long-Term Follow-Up Period.
 
e) Investigators must discuss choice of HAART regimen and timing of initiation with the medical monitor before initiating. This regimen may be supplied regionally by GSK or reimbursement will be provided.

HIV-1 RNA	X	X	X	X	X	X	
CD4+	X	X	X	X	X	X	
Plasma for Storage	X	X	X	X	X	X	
PK Sample for Storage	S	S	S	S	S	S	
Clinical Chemistry and Hematology	X	X	X	X	X	X	
Pregnancy Testing ^b	S	S	S	S	S	S	
Urinalysis	X				X	X	
Fasting: Glucose, Cholesterol (Total, HDL and LDL) and Triglycerides ^c					X	X	
PT/PTT/INR					X	X	
Contraception Counselling ^d	X	X	X	X	X	X	
HAART Dispensation ^e	X	X	X	X	X	X	

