8.6.3. Grade 3 Toxicity/Adverse Event

Participants who develop a Grade 3 AE or toxicity should be managed as follows:

- If the Investigator has compelling evidence that the Grade 3 AE or toxicity has not been caused by IP, dosing may continue after discussion with the Medical Monitor.
- Participants who develop a Grade 3 AE or toxicity, which the Investigator considers related or possibly related to the IP, should have the IP withheld and be rechecked each week until the AE returns to Grade 2. Once the AE is Grade ≤ 2 , IP may be re-started.
- Should the same Grade 3 AE recur within 28 days in the same participant, the IP should be permanently discontinued and the participant withdrawn from study.
- Participants experiencing Grade 3 AEs requiring permanent discontinuation of IP should be followed weekly until resolution of the AE and to have withdrawal study evaluations completed. A follow-up visit should be performed 4 weeks after the last dose of IP. Any participant receiving at least one dose of CAB LA and/or RPV LA who discontinue IP / Withdraw will initiate treatment with HAART and enter the LTFU Phase for 52 weeks of follow up.
- Participants with Grade 3 asymptomatic laboratory abnormalities should be investigated for all potential non-drug related causes, and, following discussion with the Medical Monitor, may continue IP if the Investigator has compelling evidence that the toxicity is not related to IP, with the exception of liver chemistry stopping criteria (See Section 8.7.1). Isolated Grade 3 lipid abnormalities do not require withdrawal of IP.

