8.11.1. Value Evidence and Outcomes Endpoints (Secondary)

- Change from Baseline (Day 1) in total “treatment satisfaction” score, and individual item scores of the HIVTSQs at Months 6, 12 (or Withdrawal).
- Change in treatment satisfaction over time (using the HIVTSQc) at Month 12 (or Withdrawal).
- Change from Baseline (Day 1) in HIVDQoL at Months 6, and 12, (or Withdrawal).

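### Protocol Section 4.2.3 sends injected discontinuers past the Withdrawal visit into a follow-up schedule without questionnaires, while the Q2M schedule, other protocol sections and the SAP expect HIVTSQ and HIVDQoL at withdrawal

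*Protocol*

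**What the plan says.** **The rule for injected participants.** Protocol Section 4.2.3 and the synopsis say of anyone who has had an injection and discontinues: "These participants will not complete a Withdrawal visit, but will instead move directly into the LTFU". The notes to the LTFU table in Section 8.1.3 add: "Every effort should be made to enter participants into the Long-Term Follow Up if they withdraw". That table covers Months 1, 3, 6, 9 and 12 and its own WD column. It lists adverse events, HIV-1 RNA, CD4+, laboratory tests, stored samples, contraception counselling and HAART. It has no row for HIVTSQs, HIVTSQc or HIVDQoL.

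**What points the other way.**
- The Q2M schedule (Section 8.1.1) marks all three questionnaires in its WD column. A footnote to that column reads "l. Or Long-Term Follow Up".
- Section 7, on premature or permanent withdrawal from the study, says that "the procedures described in the Time and Events Table for the in-clinic Withdrawal visit are to be performed".
- Section 7.1.5.3, on discontinuation of study intervention, says that "the investigator must make every effort to perform the Withdrawal Visit evaluations outlined in the Time and Events".
- Section 8.6.3 requires participants who stop for a Grade 3 event "to have withdrawal study evaluations completed", and sends injected participants to LTFU in the same bullet. Section 8.6.4 encourages the withdrawal evaluations after a Grade 4 event and also goes on to LTFU.
- The secondary questionnaire endpoints in Section 8.11.1 allow for withdrawal, for example "Change in treatment satisfaction over time (using the HIVTSQc) at Month 12 (or Withdrawal".
- SAP Section 12.3.4.1 assigns withdrawal questionnaires to the next planned questionnaire visit. Its worked example is a withdrawal at Month 8, a visit that only the Q2M schedule has. SAP Section 12.4.1 also describes a Q2M participant with a withdrawal visit at Month 12.

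**The other arm.** The DTG + RPV schedule (Section 8.1.2) has all three questionnaires at WD, and that arm has no LTFU phase.

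**Missing data.** SAP Section 9.4 imputes nothing for the health outcomes. The scoring rules in SAP Section 12.6.5 fill in missing items within a completed form, which does not help when the whole form is absent.

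**The concern.** Every Q2M participant is injected on Day 1, and anyone injected who stops for any reason is directed to LTFU. Read literally, 4.2.3 leaves the WD column of the Q2M schedule with almost nobody to apply to. Whether a Q2M discontinuer fills in the questionnaires then depends on which sentence the site reads.

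The loss would not be neutral. Section 4.3 stresses acceptability and tolerability of the injectable regimen as secondary objectives, and Section 7 lists intolerability of injections among the reasons for stopping. If those participants' forms are missing, the Q2M means describe mainly people content to continue. The loss would fall in one arm only.

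**Working it through.** The plan gives no precision or missing-data figure for the questionnaires. Its only sizing table (Protocol Section 10.2.1) concerns the primary virologic endpoint and does not bear on this point. The check is therefore a comparison of rules, followed by an illustration of size.

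**1. What each rule leaves for a Q2M participant.** Planned questionnaire visits (SAP Table 11) are Day 1, Month 6 and Month 12 for HIVTSQs and HIVDQoL, and Month 12 only for HIVTSQc.

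| Time of stopping | If 4.2.3 is followed | If withdrawal forms are collected in the Maintenance Phase (SAP 12.3.4.1) |
|---|---|---|
| Before the Month 6 forms | No HIVTSQc; no post-baseline HIVTSQs or HIVDQoL | HIVTSQs and HIVDQoL slotted to Month 6; HIVTSQc slotted to Month 12 |
| After Month 6, before Month 12 | Month 6 HIVTSQs and HIVDQoL kept; no Month 12 values; no HIVTSQc | All three slotted to Month 12 |
| After the Month 12 forms | Nothing lost | Nothing lost |

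The loss of HIVTSQc before Month 12 needs no assumption about scores.

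**2. When the SAP can use a form.** SAP Section 12.3.4.1 slots a record outside the planned visits only if it is labelled as a withdrawal or unscheduled visit and falls in the Maintenance Phase. For Q2M, SAP Table 13 ends that phase on the LTFU ART start date, inclusive. A record labelled LTFU Month 1 does not meet the labelling condition. LTFU time also runs from the last injection, so a participant who stops when the next injection is due, about 60 days later, is already past LTFU Month 1.

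**3. Illustrative size.** Let f be the share of Q2M participants whose score is lost in this way, let completers gain 3 points on HIVTSQs, and let discontinuers change by d.

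- Observed mean = 3
- Mean over everyone = (1 − f) × 3 + f × d
- Upward shift = f × (3 − d)

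| f | d = −10 | d = −20 |
|---|---|---|
| 2% | 0.02 × 13 = 0.26 | 0.02 × 23 = 0.46 |
| 5% | 0.05 × 13 = 0.65 | 0.05 × 23 = 1.15 |

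The 2% is the rate of adverse-event withdrawal in the LATTE-2 Q8W arm through Week 96 (Protocol Section 2.2). The 5%, the 3-point gain and both values of d are assumptions. So is the 0 to 66 range: 11 items scored 0 to 6 give 11 × 6 = 66, but the item list is redacted. The planned 100 participants cover both arms with no stated split, so 2% to 5% is at most 2 to 5 people.

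**The case against.** The strongest objection is that only one sentence and its synopsis copy remove the Withdrawal visit. The Q2M WD column, four other protocol sections, the endpoint definitions and the SAP all expect it. The footnote to the WD column can be read as saying that the column is completed on transition to LTFU. A reader might infer that Q2M discontinuers do drop out of these endpoints. The documents do not support that as fact, because it happens only where 4.2.3 is followed.

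This part of the objection stands, but it does not settle the matter. Section 4.2.3 is the rule specific to injected participants, and Section 7.1 refers them back to it. The Section 7 rule is worded for withdrawal from the study, whereas 4.2.3 counts LTFU as study participation. Section 7.1.5.3 is placed under virologic failure, and 8.6.3 and 8.6.4 cover adverse events. The footnote does not say which procedures apply. A site could reasonably skip the forms.

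Three further objections limit the consequences:
- **Direction.** A reader might infer that the missing participants are the least satisfied injection users. Participants also stop for virologic failure, pregnancy, prohibited medication or loss to follow-up, and those lost to follow-up would miss a Withdrawal visit in either arm. Upward bias is likely, not shown.
- **Size.** A reader might assume 10% discontinuing and shifts above 2 points. The LATTE-2 Q8W figures do not point that high. At Week 96, 115 − 108 − 5 = 2 participants had no virologic data, 1 failed for lack of efficacy and 2 withdrew for other reasons while not suppressed. That is at most 5/115 = 4.3%, over a period well beyond Month 12.
- **Comparison of arms.** One-sided loss might seem to invalidate a treatment comparison. Participants choose their arm, and no comparison is tested (Protocol Section 10.1, SAP Section 2.4). The exposure is mainly in the descriptive Q2M results. Withdrawal reasons, adverse events leading to discontinuation and injection site reactions are tabulated separately, so exits for intolerability remain visible there.

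**Conclusion.** The point holds as an unresolved contradiction with a foreseeable effect on secondary endpoints. If 4.2.3 is followed, questionnaire data are lost at Q2M discontinuation, in that arm only, and the SAP has no means of recovering them. The complete loss of HIVTSQc for anyone stopping before Month 12 follows from the schedules alone.

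The likely direction is an overstated Q2M satisfaction mean, because injection intolerance is one recognised reason for stopping. The size cannot be determined from the documents. On the assumed scores it is about 0.3 to 0.5 points at 2% discontinuing and 0.65 to 1.15 at 5%. If sites complete the WD column instead, this loss does not arise.

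**What to change.** - Reconcile Section 4.2.3 and the synopsis with Sections 7, 7.1.5.3, 8.6.3 and 8.6.4 and with the WD column and footnote of the Q2M schedule (also reproduced in the SAP).
- State that HIVTSQs, HIVTSQc and HIVDQoL are collected at the Q2M discontinuation visit, recorded as a withdrawal visit and completed on or before the LTFU ART start date. SAP Section 12.3.4.1 then slots them without change. This concerns the timing of the forms only, not the timing of therapy.
- Do not rely on questionnaires at LTFU Month 1 unless the SAP slotting rule is also changed to accept them.
- Report questionnaire completion by arm and discontinuation status. This also shows the gap that slotting cannot close: a participant who stops before Month 6 contributes HIVTSQs and HIVDQoL at Month 6 but not at Month 12.

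The cost is a small edit to the protocol and schedule, one completion table, and one extra set of forms per discontinuer.
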